9.9 Sample Size and Power Calculations

9.9.1 Sample Size and Power for Immunogenicity

Approximately 1990 participants will be enrolled in the study with the following allocated sample sizes for each age group as: 690 participants in 9-19yr age group (460 in 9-15yr and 230 in 16-19yr), 650 participants in 20-26yr age group, and 650 participants in 27-45yr age group. The overall power to claim the study success based on the dual-primary hypotheses is >0.999.

Two dual-primary hypotheses (H1 and H2) and two secondary hypotheses (H3 and H4) are considered when determine overall sample size and the sample sizes allocated to each age group. The calculations are based on the following assumptions:

- 1) HPV Types 6, 11, 16, 18, 31, 33, 45, 52, 58 responses are identical in 9-15yr, 9-19yr, and 20-26yr age groups;

- 2) HPV Types 6, 11, 16, 18, 31, 33, 45, 52, 58 seroconversion percentages are identical in 9-19yr, 20-26yr, and 27-45yr age groups;
- 3) The overall percentages of participants not eligible for per-protocol analyses for each HPV type are 15% in 9-15yr age group, 9-19yr age group, 30% in 20-26yr and 27-45yr age groups which are calculated based on:
 - percentage of the participants are initially seropositive to each HPV type
 - expected attrition rate through 1 month post Dose 3 (Visit 10)
 - expected percentage of participants excluded due to vaccinations or serology samples out of range
- 4) The standard deviations of the natural logarithm of the Visit 10 titers are no more than 1.2 for each HPV type when expressed as mMU/mL, the unitage used in previous HPV vaccine studies;
- 5) Regarding to the dual-primary hypotheses (H1 and H2), Type I error will be controlled by Bonferroni Method, i.e. one-sided 0.0125 for each hypothesis.

The estimates of exclusion rates and standard deviation are based on the data from previous qHPV vaccine and 9vHPV vaccine studies.

The overall power to establish the non-inferiority of the dual-primary endpoints: (1) cLIA GMTs in 9-19 yr vs. 20-26 yr; and (2) cLIA seroconversion percentages in 27-45yr vs. 20-26yr will be at least 99.1% and 92.9% respectively, at a level of 0.0125.

The overall power to establish the non-inferiority of the secondary endpoints: (1) cLIA seroconversion percentages in 9-19yr vs. 20-26yr and (2) cLIA GMTs in 9-15yr vs. 20-26y will be at least 98.4% and 95.8% respectively, at a level of 0.0125.

The detailed sample size and power results for immunogenicity endpoints are presented in [Table 6](#), [Table 7](#), and [Table 8](#) by age groups.

Table 6 Power for Non-Inferiority Comparison in 9-19yr Group vs. 20-26yr Group

GMT ratio (Dual-primary, H1)					
Antigen	Assumed SD	Enrolled Sample Size (9-19yr/20-26yr)	Effective Sample Size (9-19yr/20-26yr)	Power	Overall Power [†]
Each HPV Type	1.2	690/650	586/455	0.999	0.991
Seroconversion percentage difference (Secondary, H3)					
Antigen	SR	Enrolled Sample Size (9-19yr/20-26yr)	Effective Sample Size (9-19yr/20-26yr)	Power	Overall Power [†]
Each HPV Type	98%	690/650	586/455	0.998	0.984

Note: Non-inferiority margin for GMT ratio is 0.67; non-inferiority margin for seroconversion rate is -5%.

[†] Overall power is calculated by multiplying the power for each HPV type.

Table 7 Power for Non-Inferiority Comparison in 9-15yr Group vs. 20-26yr Group

GMT ratio (Secondary, H4)					
Antigen	Assumed SD	Enrolled Sample Size (9-15yr/20-26yr)	Effective Sample Size (9-15yr/20-26yr)	Power	Overall Power [†]
Each HPV Type	1.2	460/650	391/455	0.995	0.958

Note: Non-inferiority margin for GMT ratio is 0.67.

[†] Overall power is calculated by multiplying the power for each HPV type.

Table 8 Power for Non-Inferiority Comparison in 27-45yr Group vs. 20-26yr Group

Seroconversion percentage difference (Dual-primary, H2)					
Antigen	SR	Enrolled Sample Size (27-45yr/20-26yr)	Effective Sample Size (27-45yr/20-26yr)	Power	Overall Power [†]
Each HPV Type	98%	650/650	455/455	0.992	0.929

Note: Non-inferiority margin for seroconversion percentage is -5%;

[†] Overall power is calculated by multiplying the power for each HPV type.

The original GMT values are log transformed before analysis. As such, the CI for the means and the non-inferiority margin will be constructed on the natural log scale. The calculations are based on two-sample t-test and are carried out using PASS 2008. The minimum criterion for success is that the lower bound of two-sided 97.5% CI of difference between natural-log-transformed GMTs > log (0.67). Given the assumed SD of the natural-log-transformed titers at 1 month post Dose 3, this may occur when the observed difference between treatment groups is approximately log (0.82) or larger.

The calculations of power and sample sizes for seroconversion percentages are based on an asymptotic method proposed by Miettinen and Nurminen (1985) [Miettinen, O. and Nurminen, M. 1985] and are carried out using PASS 2008. The minimum criterion for success is that the lower bound of two-sided 97.5% CI of difference $> -5\%$. Given the assumed seroconversion percentage 98%, this may occur when the observed difference in response rates is approximately -3% or larger.

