9.8 Multiplicity

Figure 2 shows the multiplicity strategy for the study.

[figure not shown]

Figure 2 Multiple Strategies to Control Overall Type One Error Rate

For the dual-primary hypotheses (H1 and H2), Bonferroni method is used to control overall one-sided type I error at level of 0.025. Each of the dual-primary hypotheses has a 0.0125 one-sided type I error. The study would be successful if either H1 or H2 are met. If H1 is not met then no further testing (H3, H4) will be completed.

Fix sequence testing strategy is used to control multiplicity between dual-primary hypothesis (H1) and secondary hypotheses (H3 and H4). The testing order is as follows: H1 (GMT, 9-19yr vs.20-26yr) will be tested firstly and if H1 wins H3 (seroconversion percentages, 9-19yr vs. 20-26yr) will then be tested; if H3 wins H4 (GMT, 9-15yr vs. 20-26yr) will be tested. Each one will be tested at a level of 0.0125. If anyone failed to reject null the subsequent ones would not be tested.

Furthermore, success is required on all 9 HPV types for hypotheses testing GMT and seroconversion percentages, so no multiplicity adjustment is needed to account for the multiple HPV types.

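### The 98.4% (H3) and 95.8% (H4) powers are stand-alone figures that leave out the H1-H3-H4 testing sequence; through the sequence they are about 97.5% and 94%

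*Combined protocol and SAP*

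**What the plan says.** Section 9.8 places H1, H3 and H4 in a fixed order. On the level it says: "Each one will be tested at a level of 0.0125". On stopping it says: "If anyone failed to reject null the subsequent ones would not be tested", and, for the first step, "If H1 is not met then no further testing (H3, H4) will be completed". Within each hypothesis, "success is required on all 9 HPV types for hypotheses testing GMT and seroconversion percentages".

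Section 9.9.1 then states that power for H3 and H4 "will be at least 98.4% and 95.8% respectively, at a level of 0.0125". Tables 6 and 7 repeat these as 0.984 and 0.958. Their footnote describes the only combination that was made: "Overall power is calculated by multiplying the power for each HPV type". Neither the text nor the tables say that the figures are separate from the earlier tests in the sequence, and no power through the sequence is given.

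**The concern.** To establish H4 in this trial, three things must happen: H1 wins on all nine types, then H3 does, then H4 does. The chance of all three cannot exceed the chance of H4 alone. A figure worked out for H4 alone and introduced with *at least* therefore sets a floor where the testing order permits only a ceiling, if everything else is held at the planning values. H3 is affected in the same way, one step earlier.

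H4 is the only hypothesis confined to girls 9 to 15 years of age. Sections 2.1 and 4.1 name that group for the extension of the indication, and Section 9.9.1 says that H3 and H4 were taken into account in setting the sample size. A reader planning around H4 would naturally take 95.8% as its chance of success.

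**Working it through.** **Inputs (Sections 9.8 and 9.9.1, Tables 6 and 7).** One-sided alpha is 0.0125 for each hypothesis. Margins: "Non-inferiority margin for GMT ratio is 0.67; non-inferiority margin for seroconversion rate is -5" percentage points. "The standard deviations of the natural logarithm of the Visit 10 titers are no more than 1.2 for each HPV type"; the tables use 1.2. True GMT ratio 1, true seroconversion 98% in both groups. Effective sizes are 586/455 for H1 and H3 and 391/455 for H4. The nine types are multiplied as independent.

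**Step 1: reproduce the stand-alone figures.** For the GMT hypotheses, per-type power is Φ(−ln 0.67 / SE − z), with −ln 0.67 = 0.4005, z = 2.2414 and SE = 1.2 × √(1/n₁ + 1/n₂).

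- H1: SE = 1.2 × √(1/586 + 1/455) = 0.0750. Φ(5.341 − 2.241) = Φ(3.100) = 0.9990 per type. Ninth power 0.991. Stated 0.991.
- H4: SE = 1.2 × √(1/391 + 1/455) = 0.0828. Φ(4.840 − 2.241) = Φ(2.598) = 0.9953 per type, or 0.9952 with the noncentral t. Ninth power 0.959 or 0.958. Stated 0.958.
- H3: asymptotic Miettinen-Nurminen at 98%/98%, margin 5 points: 0.9982 per type. Ninth power 0.984. Stated 0.984.

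All three agree with the plan.

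**Step 2: bounds that need no assumption about dependence between hypotheses.** The chance that all tests succeed is at most the smallest single power, and at least 1 minus the sum of the failure probabilities (0.009, 0.016 and 0.042).

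- H3 through the sequence: from 1 − 0.009 − 0.016 = 0.975 to 0.984.
- H4 through the sequence: from 1 − 0.009 − 0.016 − 0.042 = 0.933 to 0.958.

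H4 reaches 0.958 only if every failure of H1 or H3 is also a failure of H4.

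**Step 3: best estimate.**

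- H3: 0.991 × 0.984 = 0.975.
- H1 and H4 share the whole 20-26 year group, and the 9-15 year girls are part of the 9-19 year group. The correlation of the two test statistics for one type is the ratio of the standard errors, 0.0750/0.0828 = 0.906. The bivariate normal probability that both succeed is 0.99515 per type, and its ninth power is 0.957. The H1 step therefore costs H4 only about 0.1 point (0.9586 to 0.9572).
- Treating H3 as independent of these: 0.957 × 0.984 = 0.942. A simulation of the nested groups with 400,000 runs also gives 0.942.

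| Hypothesis | Stated | Through the sequence | Loss |
|---|---|---|---|
| H3 | 98.4% | about 97.5% | 0.9 points |
| H4 | 95.8% | about 94.2% (93.3%-95.8%) | 1.6 points (at most 2.5) |

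**Step 4: sensitivity of H4 through the sequence.**

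- Smaller SD, H3 held at 98.4%: 95.5% at SD 1.17, 95.8% at 1.16, 96.2% at 1.15, 97.3% at 1.1.
- Correlation of log titers between types (an assumption; the documents give none), H3 held at 98.4%: 94.2% at 0, 94.6% at 0.3, 95.2% at 0.5, 95.9% at 0.7.
- H3 power by exact enumeration (0.992) instead of the asymptotic value: 0.957 × 0.992 = about 95.0%.

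**The case against.** The best defence is that nothing was miscalculated. The figures are right for what the footnotes define, Section 9.8 sets out the sequence openly just before, and the text speaks of power at a level of 0.0125 without claiming that it runs through the sequence. The inputs are also cautious. The SD of 1.2 is a stated maximum, and an SD about 3% lower (1.16) brings H4 back to 95.8% even through the sequence. Positively correlated types or the exact H3 power would also narrow the gap. All of this stands, and it limits the point to how the power is reported. It does not supply the missing figures: at the values printed in the tables, the sequence is still left out.

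Some stronger readings are tempting but not supported:

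- *The trial is underpowered for 9-15 year olds.* It is not: power through the sequence is at least 93.3% under any dependence between the hypotheses. These girls also make up 460 of the 690 enrolled for H1 and H3, and H4 is secondary and outside the success criterion.
- *The stated figures are powers conditional on the earlier wins.* They are marginal. Given wins on H1 and H3, with H3 treated as independent, power for H4 is 0.957/0.991 = about 96.6%.
- *H4 has 0.991 × 0.984 × 0.958 = 93.4%.* That product ignores the overlap of the H1 and H4 data.
- *The headline power above 0.999 is contradicted.* That figure concerns success on either H1 or H2, which is a different event.

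**Conclusion.** The point holds as a minor correction to the reported power. The figures of 98.4% and 95.8% are correct as stand-alone powers over nine types, but *at least* does not hold for the planned procedure at the stated planning values. The sequence lowers power to about 97.5% for H3 and about 94% for H4, so the chance of not establishing H4 is about 5.8% rather than 4.2%. Nearly all of the H4 loss comes through H3.

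The 94.2% rests on SD 1.2, 98% seroconversion, independent types, the asymptotic H3 power, and H3 independent of H1 and H4. The range of 93.3% to 95.8% takes the plan's three stated powers as given and needs no assumption about dependence between the hypotheses.

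**What to change.** In Section 9.9.1 and the footnotes to Tables 6 and 7:

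- label 98.4% and 95.8% as stand-alone powers that do not account for the testing sequence, and avoid the word conditional;
- tie *at least* to that label;
- add the power through the sequence: H3 about 97.5%; H4 about 94% (94.2% allowing for the H1/H4 overlap and treating H3 as independent; 93.3%-95.8% under any dependence between the hypotheses).

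This takes a sentence and two footnotes. The only cost is that the stated figures become slightly less favourable. Sample size, alpha, testing order and analysis stay as they are.

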9.9.2 Sample Size and Power for Safety

The probability of observing a specific AE in this study depends on the number of vaccinated participants with safety follow-up and the underlying incidence of that specific AE in the study population.

Across seven clinical studies in the 9vHPV vaccine program, 356 of 15,778 (2.3%) individuals who were administered vaccine and had safety follow-up reported a SAE; 0.044% (7 out of 15,778) reported at least one SAE determined to be vaccine related [Moreira, E. D., et al 2016].

Assuming that all 650 participants enrolled in this study will have safety follow-up, then there is a greater than 99.9% chance of observing at least one SAE; and 24.9% chance of observing at least one vaccine related SAE, on at least one of the 650 participants. If no vaccine-related SAEs are observed among the 650 participants, this study will provide 95% confidence that the underlying percentage of participants with vaccine-related SAE is $<0.46\%$ (1 in every 217 participants) among vaccinated participants. This is based on calculation of a 1-sided 97.5% upper confidence limit of a binomial proportion using the exact binomial method of Clopper and Pearson [Clopper, C. J. 1934].

9.10 Subgroup Analyses

Age groups, 9-19yr, 20-26yr and 27-45yr will be subgroup factors for this study. Age group 9-15 yr will also be analyzed for the secondary immunogenicity and safety objectives.

9.11 Compliance (Medication Adherence)

Compliance is defined in this study as receipt of all scheduled study vaccinations. To summarize compliance, the numbers of participants who receive each vaccination will be tabulated. Compliance with the planned vaccination schedule (Visit 1, Visit 4 and Visit 8) will be described by histograms of actual intervals between vaccinations relative to the expected interval.

9.12 Extent of Exposure

As indicated in Section 8.1.11, each study participant is planned to be administered 0.5 mL of 9vHPV vaccine at each vaccination visit. Thus, each participant is expected to be administered a total of 1.5 mL of 9vHPV vaccine.

10. Supporting Documentation and Operational Considerations

10.1 Appendix 1: Regulatory, Ethical and Study Oversight Considerations

Code of Conduct for Clinical Trials

**Merck Sharp & Dohme LLC, Rahway, NJ, USA (MSD)
Code of Conduct for Interventional Clinical Trials**

I. Introduction

A. Purpose

MSD, through its subsidiaries, conducts clinical trials worldwide to evaluate the safety and effectiveness of our products. As such, we are committed to designing, implementing, conducting, analyzing, and reporting these trials in compliance with the highest ethical and scientific standards. Protection of participants in clinical trials is the overriding concern in the design and conduct of clinical trials. In all cases, MSD clinical trials will be conducted in compliance with local and/or national regulations (including all applicable data protection laws and regulations), and International Council for Harmonisation Good Clinical Practice (ICH-GCP), and also in accordance with the ethical principles that have their origin in the Declaration of Helsinki.

B. Scope

Highest ethical and scientific standards shall be endorsed for all clinical interventional investigations sponsored by MSD irrespective of the party (parties) employed for their execution (e.g., contract research organizations, collaborative research efforts). This Code is not intended to apply to trials that are observational in nature, or which are retrospective. Further, this Code does not apply to investigator-initiated trials, which are not under the full control of MSD.

II. Scientific Issues

A. Trial Conduct

1. Trial Design

Except for pilot or estimation trials, clinical trial protocols will be hypothesis-driven to assess safety, efficacy and/or pharmacokinetic or pharmacodynamic indices of MSD or comparator products. Alternatively, MSD may conduct outcomes research trials, trials to assess or validate various endpoint measures, or trials to determine patient preferences, etc.

The design (i.e., participant population, duration, statistical power) must be adequate to address the specific purpose of the trial and shall respect the data protection rights of all participants, trial site staff and, where applicable, third parties. All trial protocols are and will be assessed for the need and capability to enroll underrepresented groups. Participants must meet protocol entry criteria to be enrolled in the trial.

2. Site Selection

MSD's clinical trials are conducted globally in many different countries and in diverse populations, including people of varying age, race, ethnicity, gender, and accounting for other potential disease related factors. MSD selects investigative sites based on medical expertise, access to appropriate participants, adequacy of facilities and staff, previous performance in clinical trials, as well as budgetary considerations. Prior to trial initiation, sites are evaluated by MSD personnel (or individuals acting on behalf of MSD) to assess the ability to successfully conduct the trial.

Where appropriate, and in accordance with regulatory authority guidance, MSD will make concerted efforts to raise awareness of clinical trial opportunities in various communities. MSD will seek to engage underrepresented groups and those disproportionately impacted by the disease under study. MSD will support clinical trial investigators to enroll underrepresented groups and expand access to those who will ultimately use the products under investigation.

3. Site Monitoring/Scientific Integrity

Investigative trial sites are monitored to assess compliance with the trial protocol and Good Clinical Practice (GCP). MSD reviews clinical data for accuracy, completeness, and consistency. Data are verified versus source documentation according to standard operating procedures. Per MSD policies and procedures, if potential fraud, scientific/research misconduct, privacy incidents/breaches or Clinical Trial-related Significant Quality Issues are

reported, such matters are investigated. When necessary, appropriate corrective and/or preventative actions are defined and regulatory authorities and/or ethics review committees are notified.

B. Publication and Authorship

Regardless of trial outcome, MSD commits to publish the primary and secondary results of its registered trials of marketed products in which treatment is assigned, according to the pre-specified plans for data analysis. To the extent scientifically appropriate, MSD seeks to publish the results of other analyses it conducts that are important to patients, physicians, and payers. Some early phase or pilot trials are intended to be hypothesis-generating rather than hypothesis testing; in such cases, publication of results may not be appropriate since the trial may be underpowered and the analyses complicated by statistical issues such as multiplicity.

MSD's policy on authorship is consistent with the recommendations published by the International Committee of Medical Journal Editors (ICMJE). In summary, authorship should reflect significant contribution to the design and conduct of the trial, performance or interpretation of the analysis, and/or writing of the manuscript. All named authors must be able to defend the trial results and conclusions. MSD funding of a trial will be acknowledged in publications.

III. Participant Protection

A. Regulatory Authority and Ethics Committee Review (Institutional Review Board [IRB]/Independent Ethics Committee [IEC])

All protocols and protocol amendments will be submitted by MSD for regulatory authority acceptance/authorization prior to implementation of the trial or amendment, in compliance with local and/or national regulations.

The protocol, protocol amendment(s), informed consent form, investigator's brochure, and other relevant trial documents must be reviewed and approved by an IRB/IEC before being implemented at each site, in compliance with local and/or national regulations. Changes to the protocol that are required urgently to eliminate an immediate hazard and to protect participant safety may be enacted in anticipation of ethics committee approval. MSD will inform regulatory authorities of such new measures to protect participant safety, in compliance with local and/or national regulations.

B. Safety

The guiding principle in decision-making in clinical trials is that participant welfare is of primary importance. Potential participants will be informed of the risks and benefits of, as well as alternatives to, trial participation. At a minimum, trial designs will take into account the local standard of care.

All participation in MSD clinical trials is voluntary. Participants enter the trial only after informed consent is obtained. Participants may withdraw from an MSD trial at any time, without any influence on their access to, or receipt of, medical care that may otherwise be available to them.

C. Confidentiality

MSD is committed to safeguarding participant confidentiality, to the greatest extent possible, as well as all applicable data protection rights. Unless required by law, only the investigator, Sponsor (or individuals acting on behalf of MSD), ethics committee, and/or regulatory authorities will have access to confidential medical records that might identify the participant by name.

D. Genomic Research

Genomic research will only be conducted in accordance with a protocol and informed consent authorized by an ethics committee.

IV. Financial Considerations

A. Payments to Investigators

Clinical trials are time- and labor-intensive. It is MSD's policy to compensate investigators (or the sponsoring institution) in a fair manner for the work performed in support of MSD trials. MSD does not pay incentives to enroll participants in its trials. However, when enrollment is particularly challenging, additional payments may be made to compensate for the time spent in extra recruiting efforts.

MSD does not pay for participant referrals. However, MSD may compensate referring physicians for time spent on chart review and medical evaluation to identify potentially eligible participants.

B. Clinical Research Funding

Informed consent forms will disclose that the trial is sponsored by MSD, and that the investigator or sponsoring institution is being paid or provided a grant for performing the trial. However, the local ethics committee may wish to alter the wording of the disclosure statement to be consistent with financial practices at that institution. As noted above, all publications resulting from MSD trials will indicate MSD as a source of funding.

C. Funding for Travel and Other Requests

Funding of travel by investigators and support staff (e.g., to scientific meetings, investigator meetings, etc.) will be consistent with local guidelines and practices.

V. Investigator Commitment

Investigators will be expected to review MSD's Code of Conduct as an appendix to the trial protocol, and in signing the protocol, agree to support these ethical and scientific standards.

Financial Disclosure

Financial Disclosure requirements are outlined in the US Food and Drug Administration Regulations, Financial Disclosure by Clinical Investigators (21 CFR Part 54). It is the Sponsor's responsibility to determine, based on these regulations, whether a request for Financial Disclosure information is required. It is the investigator's/subinvestigator's responsibility to comply with any such request.

The investigator/subinvestigator(s) agree, if requested by the Sponsor in accordance with 21 CFR Part 54, to provide his/her financial interests in and/or arrangements with the Sponsor to allow for the submission of complete and accurate certification and disclosure statements. The investigator/subinvestigator(s) further agree to provide this information on a Certification/Disclosure Form, commonly known as a financial disclosure form, provided by the Sponsor. The investigator/subinvestigator(s) also consent to the transmission of this information to the Sponsor in the United States for these purposes. This may involve the transmission of information to countries that do not have laws protecting personal data.

Data Protection

Participants will be assigned a unique identifier by the Sponsor. Any participant records or datasets that are transferred to the Sponsor will contain the identifier only; participant names or any information which would make the participant identifiable will not be transferred.

The participant must be informed that his/her personal study-related data will be used by the Sponsor in accordance with local data protection law. The level of disclosure must also be explained to the participant.

The participant must be informed that his/her medical records may be examined by Clinical Quality Assurance auditors or other authorized personnel appointed by the Sponsor, by appropriate IRB/IEC members, and by inspectors from regulatory authorities.

Confidentiality of Data

By signing this protocol, the investigator affirms to the Sponsor that information furnished to the investigator by the Sponsor will be maintained in confidence, and such information will be divulged to the IRB, IEC, or similar or expert committee; affiliated institution and employees, only under an appropriate understanding of confidentiality with such board or committee, affiliated institution and employees. Data generated by this study will be

considered confidential by the investigator, except to the extent that it is included in a publication as provided in the Publications section of this protocol.

Confidentiality of Participant Records

By signing this protocol, the investigator agrees that the Sponsor (or Sponsor representative), IRB/IEC, or regulatory authority representatives may consult and/or copy study documents in order to verify worksheet/CRF data. By signing the consent form, the participant agrees to this process. If study documents will be photocopied during the process of verifying worksheet/CRF information, the participant will be identified by unique code only; full names/initials will be masked prior to transmission to the Sponsor.

By signing this protocol, the investigator agrees to treat all participant data used and disclosed in connection with this study in accordance with all applicable privacy laws, rules and regulations.

Confidentiality of IRB/IEC Information

The Sponsor is required to record the name and address of each IRB/IEC that reviews and approves this study. The Sponsor is also required to document that each IRB/IEC meets regulatory and ICH GCP requirements by requesting and maintaining records of the names and qualifications of the IRB/IEC members and to make these records available for regulatory agency review upon request by those agencies.

Committees Structure

Executive Oversight Committee

The Executive Oversight Committee (EOC) is comprised of members of Sponsor Senior Management. The EOC will receive and decide upon any recommendations made by the Data Monitoring Committee (DMC) regarding the study.

Data Monitoring Committee

To supplement the routine study monitoring outlined in this protocol, an external DMC will monitor the interim data from this study. The voting members of the committee are external to the Sponsor. The members of the DMC must not be involved with the study in any other way (eg, they cannot be study investigators) and must have no competing interests that could affect their roles with respect to the study.

The DMC will make recommendations to the EOC regarding steps to ensure both participant safety and the continued ethical integrity of the study. Also, the DMC will review interim study results, consider the overall risk and benefit to study participants (see Section 9.7 Interim Analyses) and recommend to the EOC whether the study should continue in accordance with the protocol.

Specific details regarding composition, responsibilities, and governance, including the roles and responsibilities of the various members and the Sponsor protocol team; meeting facilitation; the study governance structure; and requirements for and proper documentation of DMC reports, minutes, and recommendations will be described in the DMC charter that is reviewed and approved by all the DMC members.

Publication Policy

The results of this study may be published or presented at scientific meetings. The Sponsor will comply with the requirements for publication of study results. In accordance with standard editorial and ethical practice, the Sponsor will generally support publication of multicenter studies only in their entirety and not as individual site data. In this case, a coordinating investigator will be designated by mutual agreement.

If publication activity is not directed by the Sponsor, the investigator agrees to submit all manuscripts or abstracts to the Sponsor before submission. This allows the Sponsor to protect proprietary information and to provide comments.

Authorship will be determined by mutual agreement and in line with International Committee of Medical Journal Editors authorship requirements.

Compliance with Study Registration and Results Posting Requirements

Under the terms of the Food and Drug Administration Amendments Act (FDAAA) of 2007 and the European Medicines Agency (EMA) clinical trial Directive 2001/20/EC, the Sponsor of the study is solely responsible for determining whether the study and its results are subject to the requirements for submission to <http://www.clinicaltrials.gov>, www.clinicaltrialsregister.eu or other local registries. MSD, as Sponsor of this study, will review this protocol and submit the information necessary to fulfill these requirements. MSD entries are not limited to FDAAA or the EMA clinical trial directive mandated trials. Information posted will allow participants to identify potentially appropriate studies for their disease conditions and pursue participation by calling a central contact number for further information on appropriate study locations and site contact information.

By signing this protocol, the investigator acknowledges that the statutory obligations under FDAAA, the EMA clinical trials directive or other locally mandated registries are that of the Sponsor and agrees not to submit any information about this study or its results to those registries.

Compliance with Law, Audit, and Debarment

By signing this protocol, the investigator agrees to conduct the study in an efficient and diligent manner and in conformance with this protocol; generally accepted standards of GCP (eg, International Conference on Harmonization of Technical Requirements for Registration of Pharmaceuticals for Human Use Good Clinical Practice: Consolidated Guideline and other generally accepted standards of GCP); and all applicable federal, state and local laws, rules and regulations relating to the conduct of the clinical study.

The Code of Conduct, a collection of goals and considerations that govern the ethical and scientific conduct of clinical investigations sponsored by MSD, is provided in this appendix under the Code of Conduct for Clinical Trials.

The investigator agrees not to seek reimbursement from participants, their insurance providers or from government programs for procedures included as part of the study reimbursed to the investigator by the Sponsor.

The investigator will promptly inform the Sponsor of any regulatory authority inspection conducted for this study.

The investigator agrees to provide the Sponsor with relevant information from inspection observations/findings to allow the Sponsor to assist in responding to any citations resulting from regulatory authority inspection, and will provide the Sponsor with a copy of the proposed response for consultation before submission to the regulatory authority.

Persons debarred from conducting or working on clinical studies by any court or regulatory authority will not be allowed to conduct or work on this Sponsor's studies. The investigator will immediately disclose in writing to the Sponsor if any person who is involved in conducting the study is debarred or if any proceeding for debarment is pending or, to the best of the investigator's knowledge, threatened.

Data Quality Assurance

All participant data relating to the study will be recorded on printed or electronic CRF unless transmitted to the Sponsor or designee electronically (eg, laboratory data). The investigator or qualified designee is responsible for verifying that data entries are accurate and correct by physically or electronically signing the CRF.

Detailed information regarding Data Management procedures for this protocol will be provided separately.

The investigator must maintain accurate documentation (source data) that supports the information entered in the CRF.

The investigator must permit study-related monitoring, audits, IRB/IEC review, and regulatory agency inspections and provide direct access to source data documents.

Study documentation will be promptly and fully disclosed to the Sponsor by the investigator upon request and also shall be made available at the study site upon request for inspection, copying, review and audit at reasonable times by representatives of the Sponsor or any regulatory authorities. The investigator agrees to promptly take any reasonable steps that are requested by the Sponsor or any regulatory authorities as a result of an audit or inspection to cure deficiencies in the study documentation and worksheets/CRFs.

The Sponsor or designee is responsible for the data management of this study including quality checking of the data.

Study monitors will perform ongoing source data review and verification to confirm that data entered into the CRF by authorized site personnel are accurate, complete, and verifiable from source documents; that the safety and rights of participants are being protected; and that the study is being conducted in accordance with the currently approved protocol and any other study agreements, ICH GCP, and all applicable regulatory requirements.

Records and documents, including signed ICF, pertaining to the conduct of this study must be retained by the investigator for 15 years after study completion unless local regulations or institutional policies require a longer retention period. No records may be destroyed during

the retention period without the written approval of the Sponsor. No records may be transferred to another location or party without written notification to the Sponsor.

Source Documents

Source documents provide evidence for the existence of the participant and substantiate the integrity of the data collected. Source documents are filed at the investigator's site.

Data reported on the CRF or entered in the eCRF that are transcribed from source documents must be consistent with the source documents or the discrepancies must be explained. The investigator may need to request previous medical records or transfer records, depending on the study. Also, current medical records must be available.

Study and Site Closure

The Sponsor or its designee may stop the study or study site participation in the study for medical, safety, regulatory, administrative, or other reasons consistent with applicable laws, regulations, and GCP.

In the event the Sponsor prematurely terminates a particular study site, the Sponsor will promptly notify that study site's IRB/IEC.

